### 7.2. Modification of Dose and/or Treatment Schedule

Starting on Day 8 of treatment, dose reduction to ALKS 8700 231 mg BID is permitted at the Investigator's discretion for subjects who are unable to tolerate ALKS 8700 462 mg BID. Once a subject has stabilized after dose reduction, attempts should again be made to achieve and maintain the target maintenance dose of ALKS 8700 462 mg BID. If a subject remains unable to tolerate ALKS 8700 462 mg BID after 1 month on treatment (i.e., by Visit 4), further dose reduction will not be permitted, and the subject will be discontinued from the study.

In the event of a suspected relapse (new symptoms or worsening symptoms), subjects will be asked to call the treating neurologist within 48 to 72 hours of the onset of the symptoms to determine the necessity of an Unscheduled Relapse Visit. An Unscheduled Relapse Visit will be conducted as described in Section 5.4. Further instruction is also provided in Section 7.2.2.

Should progressive multifocal leukoencephalopathy (PML) be suspected by the treating neurologist based on symptoms or signs during the relapse visit, study treatment will be withheld and an appropriate diagnostic work-up should be performed as soon as possible (within 14 days of the relapse visit). If PML is excluded based on the diagnostic work-up, the subject may resume taking study treatment if approved by the Medical Monitor. If the diagnostic work-up exceeds 14 days, the subject will be discontinued from the study. Should a diagnosis of PML be confirmed, the subject will be discontinued from the study and provided with appropriate medical care.

If serious infection occurs, study treatment should be withheld until it has resolved.

CONFIDENTIAL

The information contained herein may not be used, disclosed, or published without the written consent of Biogen MA Inc.

Study treatment must also be temporarily withheld if any of the following laboratory parameters meet the following threshold limits:

- AST or ALT  $> 3 \times \text{ULN}$ ; confirmed by repeat testing as soon as possible. If the value remains  $> 3 \times \text{ULN}$  for  $\geq 4$  weeks after discontinuation of study treatment, the subject must permanently discontinue study treatment.

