## 11.3. Monitoring and Recording Events

### 11.3.1. Adverse Events

Any AE experienced by the subject between the time of first dose of study treatment and until the completion of the safety follow-up visit (Visit 16) is to be recorded on the eCRF, regardless of the severity of the event or its relationship to study treatment. At each study visit, the Investigator will assess the subject for AEs and will record any new AEs or updates to previously reported AEs on the eCRF. Any AE or SAE having an onset after the safety follow-up visit will not be collected or reported unless the Investigator feels that the event may be related to the study treatment.

The following events will not be collected as AEs:

- Disability progression based on the EDSS is captured in the MS efficacy assessments and is not to be recorded as an AE unless the event meets the definition of an SAE (see Section 11.1.2). Events of MS relapse, whether protocol-defined or not, are to be recorded as AEs (or as SAEs [see Section 11.1.2]).
- Illnesses present prior to the subject signing the ICF are considered to be pre-existing conditions and are documented on the medical history eCRF. Pre-existing conditions that worsen during the study are entered on the AE eCRF.
- Pregnancy is not considered an AE, although a subject will be withdrawn from the study if a pregnancy occurs. As described in Section 11.4.1, the pregnancy must be reported to Biogen and additional follow-up may be required.

CONFIDENTIAL

The information contained herein may not be used, disclosed, or published without the written consent of Biogen MA Inc.

The Investigator will assess all AEs regarding any causal relationship to the study treatment (see Section 11.2.2), the severity of the event, action taken, and subject outcome.

The criteria set out in Section 11.2.3 should be used to guide the assessment of severity.

All AEs will be followed until resolution, until deemed stable by the Investigator, or until the subject is deemed by the Investigator to be lost to follow-up.

For clinical study safety reporting purposes, the version of the Investigator's Brochure at the time of the event occurrence will be used as the reference document to designate event expectedness.

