#### **11.4.2. Overdose**

An overdose is any dose of study treatment administered to a subject or taken by a subject that exceeds the dose assigned to the subject according to the protocol. Overdoses are not considered AEs and should not be recorded as an AE on the eCRF; however, all overdoses must be recorded on an Overdose form and faxed or emailed to the Sponsor within 24 hours of the site becoming aware of the overdose. An overdose must be reported to the Sponsor even if the overdose does not result in an AE. If an overdose results in an AE, the AE must be recorded. If an overdose results in an SAE, both the SAE and Overdose forms must be completed and faxed or emailed to the Sponsor. All study treatment-related dosing information must be recorded on the dosing eCRF.

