1.1. Study Objectives

The objectives of this study are: 1) to evaluate the long-term safety and tolerability of ALKS 8700 (also known as BIIB098 and diroximel fumarate) for up to 96 weeks of treatment in adult subjects with RRMS and 2) to evaluate treatment effect over time in adult subjects with RRMS treated with ALKS 8700.

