3.6.2. Adverse Events

All adverse events (AEs) will be coded by System Organ Class and Preferred Term using the Medical Dictionary for Regulatory Activities MedDRA version 20.1 or higher. The verbatim term will be included in the AE listings.

AEs will be identified as emerging in the treatment period and the follow up period. During the treatment period, an AE will be considered as treatment-emergent AE (TEAE) if the event starts or worsens on or after the date of first dose of study drug in the current study. The Treatment Period is defined as the first dose start date to the date of end of treatment (EOT) in the current study, inclusive.

During the follow up period, post-discontinuation emergent AEs (PDEAEs), defined as AEs that started or worsened after date of the EOT visit, will be summarized. For PDEAEs, the greatest severity before or on the date of the EOT visit will be used as the benchmark for the comparison

of the AEs occurring during the follow up period. The Follow-up Period is defined as the period between the date of the EOT visit plus 1 day and the last study visit, inclusive.

An overview table, including number of subjects with TEAEs, serious AEs (SAEs), AEs leading to study discontinuation, study drug-related TEAEs, and PDEAEs will be provided. Adverse events leading to study discontinuation and SAEs leading to death will be summarized in the period when the discontinuation or death occurred.

The following summary tables will be provided for the treatment period by enrollment group and overall:

- TEAEs by System Organ Class and Preferred Term
- TEAEs by System Organ Class, Preferred Term, and severity
- TEAEs by System Organ Class, Preferred Term, and relationship
- Study drug related TEAEs by System Organ Class and Preferred Term
- TEAEs experienced by $\geq 5\%$ of subjects by System Organ Class and Preferred Term
- SAEs by System Organ Class and Preferred Term
- AEs leading to study discontinuation by System Organ Class and Preferred Term
- Adverse Events of Special Interest by System Organ Class and Preferred Term

In addition, an AE overview table and AEs by System Organ Class and Preferred Term for PDEAEs during the Follow-up Period will be provided.

All AE tables will be sorted by System Organ Class and then Preferred Term in decreasing frequency based on all subjects in the Safety Population.

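### Tolerability is part of the first objective, but the SAP counts only AEs that end in discontinuation and plans no count of dose reductions or interruptions

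*SAP*

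**What the plan says.** SAP 1.1 gives the first objective as "to evaluate the long-term safety and tolerability of ALKS 8700" over up to 96 weeks; Protocol 4 agrees.

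Protocol 7.2 (with the same rule in Protocol 5.3 and SAP 1.2) states that from Day 8 "dose reduction to ALKS 8700 231 mg BID is permitted at the Investigator's discretion for subjects who are unable to tolerate" 462 mg twice daily, followed by attempts to return to that dose. If intolerance of the target dose persists after one month, by Visit 4, "further dose reduction will not be permitted, and the subject will be discontinued from the study".

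Protocol 7.2 also provides for holds during a serious infection and while PML is being ruled out, and adds: "Study treatment must also be temporarily withheld if any of the following laboratory parameters meet the following threshold limits". The parameters are AST/ALT, lymphocytes, eGFR and the urine albumin to creatinine ratio.

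On data capture, Protocol 11.3.1 has the Investigator assess each AE for causality and for "the severity of the event, action taken, and subject outcome". Protocol 11.4.2 says: "All study treatment-related dosing information must be recorded on the dosing eCRF".

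On analysis, the SAP 3.6.2 list includes "AEs leading to study discontinuation by System Organ Class and Preferred Term", and SAP 3.6.3 repeats discontinuations regardless of treatment emergence. SAP 3.6.4 restricts the GI tolerability category to events that are serious or end in discontinuation. SAP 3.4 summarises days on drug, counted from first to last dose inclusive, and a ratio of capsules taken to capsules expected. Protocol 12.6 names SAEs and AEs resulting in treatment discontinuation alongside the TEAE table.

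**The concern.** Being unable to stay on the target dose is a direct measure of tolerability, and the protocol makes it the ground for a dose reduction. Protocol 3.3 presents GI tolerability as the recognised problem with DMF and a possible improvement there as the rationale for this drug. A subject reduced in the first weeks and later returned to 462 mg twice daily has shown temporary intolerance. A subject whose treatment was held has had an interruption. Neither fact is counted in any planned summary. The study could therefore report on tolerability without saying how often the target dose could not be kept up, even for a time.

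**Working it through.** The plan states no figure on this point, and there is no formal sample size calculation, so there is nothing to reproduce. The check has three parts.

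**1. Is there a planned summary of reductions or interruptions anywhere?**

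| Place | What it summarises | Reduction or interruption counted? |
|---|---|---|
| SAP 3.1.2 Disposition | Completion, discontinuation, reasons | No |
| SAP 3.1.3 Deviations | Intake under 70% or over 105%, other categories | No |
| SAP 3.4 Adherence and exposure | Capsule ratio, days first to last dose | No |
| SAP 3.6.2 and 3.6.3 AEs | TEAEs by SOC/PT, severity and relationship; drug-related; at least 5%; SAEs; discontinuation; special interest | No |
| SAP 3.6.4 GI tolerability | Serious, or ending in discontinuation | No; a non-serious GI event that led only to a reduction falls outside |
| SAP 5 Changes from protocol | COVID-19 only | No |
| Protocol 12.6 | TEAEs, SAEs, treatment discontinuation | No |

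**2. Would exposure or adherence show it indirectly?**

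Inputs from the protocol: 96 weeks; two 231 mg capsules twice daily, so 4 capsules a day at the target dose and 2 a day when reduced; reduction possible from Day 8; Visit 4 at Day 29. Assumption: one hold of 28 days, for illustration only.

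- Treatment days: 96 × 7 = 672.
- Expected capsules: 672 × 4 = 2688. With the Day 1–7 titration: 7 × 2 + 665 × 4 = 2674.
- Reduced on Days 8–28: 21 × 2 = 42 capsules fewer. Adherence (2688 − 42)/2688 = 98.4%. It is 100% if the expected count is lowered to the reduced dose; SAP 3.4 does not say which applies.
- Held for 28 days: 28 × 4 = 112 capsules fewer. Adherence (2688 − 112)/2688 = 95.8%.
- Both: (2688 − 154)/2688 = 94.3%; with titration (2674 − 154)/2674 = 94.2%.
- Days on study drug for a subject who completes: 672 in every case.
- Days fully off drug to reach the 70% deviation limit: 0.30 × 2688/4 = 201.6, or 0.30 × 2674/4 = 200.6 with titration.

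A subject with both a reduction and a four-week hold thus looks like one who missed a few capsules.

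**3. Who is actually left uncounted?**

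Under the Visit 4 rule, lasting early intolerance ends in discontinuation and is tabulated if the recorded reason is an AE. That leaves mainly subjects reduced early who regained the target dose, plus subjects with an interruption. For laboratory holds there is a further step: under Protocol 11.1.1 an abnormal result is an AE only if it meets SAE criteria, needs corrective therapy or is judged clinically significant. A hold is not itself on that list, so a laboratory hold may have no AE attached.

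**The case against.** The strongest reply is that little is lost. SAP 3.6.2 lists eight treatment-period tables, and an AE that led to a reduction is counted in those by SOC/PT, severity and relationship; all AEs are listed. Most hold triggers are summarised elsewhere: serious infections as SAEs and as events of special interest, lymphocytes below 0.5 × 10⁹/L and raised ALT/AST in SAP 3.6.5. The study is open-label and descriptive, the SAP matches Protocol 12.6, and mock tables and specifications sit in separate documents that may hold such displays.

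Most of this is right, and it limits the point. A reader might infer that intolerance short of discontinuation is not reported at all. The documents do not support that: the event is reported, and only its link to a dose change is not. A reader might also infer that the results will make the target dose look better tolerated than it was. That does not follow either, because the discontinuation count is unaffected and persistent early intolerance is routed into it.

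What remains is that the SAP does not commit to any count of reductions or interruptions. Two of the hold triggers, eGFR and the urine albumin to creatinine ratio, have no criterion in SAP Table 2. Unseen table shells may fill the gap but do not pre-specify it.

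The reply also notes, fairly, that the eCRF is not available. The protocol says action taken is assessed, and its sentence on the dosing eCRF stands in the overdose section; neither proves that reduction and interruption are separate coded categories.

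**Conclusion.** The gap is real and narrow. Followed as written, the plan never reports how many subjects needed a dose reduction for intolerance, how many of those returned to the target dose, or how many had an interruption, although tolerability is part of the first objective. No estimate, error rate or sample size is affected; what suffers is the completeness of the tolerability result.

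The size of the uncounted group cannot be derived. The documents give no rate for dose reduction, interruption or AE discontinuation in this population, and entry features (rollover subjects finished an earlier study; de novo subjects with recent significant GI symptoms or a past tolerability discontinuation of Tecfidera are excluded) make borrowed rates unreliable. Any percentage would reflect the rates chosen, so none is given. The 94% to 100% adherence range shows only that the planned summaries would not expose these subjects; it rests on the assumed 28-day hold and on the Visit 4 rule being followed.

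**What to change.** - **SAP 3.6.2:** add TEAEs leading to dose reduction, and TEAEs leading to interruption, each by SOC and PT.
- **SAP 3.4:** add the number and percentage of subjects with at least one reduction for intolerance (leaving out the planned Day 1–7 titration), the number who returned to the target dose, and the number with at least one interruption, by enrollment group and overall. Take interruptions from the dosing data as well as the AE data, so that laboratory holds without an AE are included. State how expected capsules are counted during a reduction or hold.
- **Presentation:** show these beside AE discontinuations as the tolerability result. In the same edit, reconcile the SAP's AEs leading to study discontinuation with Protocol 12.6, which refers to treatment discontinuation; Protocol 5.2 and 8.1 treat the two as different.

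The cost is SAP wording and a few descriptive tables. It depends on the action-taken and dosing fields holding usable categories, which should be checked against the eCRF first. No dose or clinical rule changes.

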3.6.3. Deaths, Serious and Other Significant Adverse Events

The number and percentage of subjects with at least one SAE (regardless treatment emergent or not) will be summarized by System Organ Class and Preferred Term for the Safety Population. Deaths and AEs leading to discontinuation (regardless treatment emergent or not) will be summarized similarly.

Supporting listings of serious AEs and AEs leading to study discontinuations will be provided. Subjects who died during the study will also be listed.

3.6.4. Adverse Events of Special Interest

Adverse events in the following categories of interest will be presented by system organ class and preferred terms:

- Anaphylaxis and Angioedema (serious events only)
- Infections (including progressive multifocal leukoencephalopathy (PML) and opportunistic infections) (serious events)
- Opportunistic infections
- Lymphopenia and Lymphopenia (lymphocyte relevant)
- Liver injury
- Malignancies
- Pre-malignant conditions
- Renal Injury
- Cardiac Disorder
- Gastrointestinal Tolerability AEs (serious or leading to discontinuation)
- Abuse potential

Supportive AE listing will be provided for each special interest group.

3.6.5. Clinical Laboratory Parameters

Laboratory parameters will be presented in conventional units. Only scheduled laboratory parameters will be included in the summaries. All laboratory data, including those collected at unscheduled visits, will be included in the listings. Laboratory results (baseline and change from baseline) for chemistry and hematology parameters for each visit during the entire study will be summarized. Percent change of lymphocyte count for each visit will be summarized.

For urinalysis, the number and percentage of subjects with abnormalities at any post-baseline visit will be summarized. In addition, the number and percentage of subjects with values considered potentially clinically significant (PCS) occurring at any post-baseline visit for selected parameters will be summarized.

Clinical laboratory test values, scheduled or unscheduled, will be considered PCS if they meet PCS criteria listed in [Table 2](#). The percentages will be calculated relative to the number of

subjects with available non-PCS baseline values with respect to the specific criterion and at least 1 post-baseline assessment. The numerator is the total number of subjects with a non-PCS baseline value with respect to the specific criterion and at least 1 post-baseline PCS value. A supportive listing will present all values for a parameter for subjects with at least one PCS value for that parameter.

Shift tables for shift from baseline to any post baseline visits during treatment period will be provided for selected chemistry, hematology, and urinalysis parameters with conventional reference limits (limits provided by the performing laboratories) for the Safety Population.

The following graphical displays will be presented by enrollment group and overall:

- Mean along with the corresponding standard error (SE) for selected chemistry and hematology laboratory parameters.
- Boxplots will be used to display summary statistics for the last assessment, maximum and minimum change from baseline values for selected chemistry and hematology laboratory parameters.

Pregnancy and drug test data will be listed.

Table 2: Criteria for Potentially Clinically Significant (PCS) Laboratory Parameters

Category	Parameter	Criteria
Hematology	Hematocrit	$\leq 32\%$ and 3 point decrease from baseline (Female) $\leq 37\%$ and 3 point decrease from baseline (Male)
	Hemoglobin	≤ 9.5 g/dL (Female) ≤ 11.5 g/dL (Male)
	Neutrophils	$< 1.5 \times 10^3/\mu\text{L}$
	Platelets	$< 75.1 \times 10^3/\mu\text{L}$ $\geq 700 \times 10^3/\mu\text{L}$
	WBCs - total, differential (absolute)	$\leq 2.8 \times 10^3/\mu\text{L}$ $\geq 16 \times 10^3/\mu\text{L}$
	lymphocytes	$< 0.5 \times 10^9/\text{L}$
	Eosinophils	$> 1.0 \times 10^3 \text{ cells}/\mu\text{L}$
Chemistry	ALT	$\geq 3 \times \text{ULN}$
	Albumin	< 2.5 g/dL
	ALK-P	$\geq 3 \times \text{ULN}$
	AST	$\geq 3 \times \text{ULN}$
	Bicarbonate	< 15 mmol/L > 31 mmol/L
	BUN	> 30 mg/dL

Category	Parameter	Criteria
	Calcium	< 8.2 mg/dL > 12 mg/dL
	Chloride	\leq 90 mmol/L \geq 118 mmol/L
	Creatine Kinase	$> 3 \times$ ULN
	Creatinine	\geq 2 mg/dL
	Gamma Glutamyltransferase	$\geq 3 \times$ ULN
	Glucose	< 50 mg/dL > 200 mg/dL
	HDL Cholesterol	\leq 30 mg/dL
	Lactate Dehydrogenase	$> 3 \times$ ULN
	LDL Cholesterol	\geq 160 mg/dL
	Phosphate	< 2 mg/dL > 5 mg/dL
	Potassium	< 3 mmol/L > 5.5 mmol/L
	Prolactin	$> 1 \times$ ULN
	Sodium	< 130 mmol/L > 150 mmol/L
	Thyroid stimulating hormone (TSH)	$> 5.5 \mu\text{IU}/\text{mL}$
	Total Bilirubin	\geq 2 mg/dL
	Total Cholesterol	$> 300 \text{ mg/dL}$
	Triglycerides	$\geq 120 \text{ mg/dL}$ (Female) $\geq 160 \text{ mg/dL}$ (Male)
	Uric Acid	$> 9 \text{ mg/dL}$ $> 8 \text{ mg/dL}$ (Female) $> 10 \text{ mg/dL}$ (Male)
Urinalysis	Glucose	at least 2+
	Protein	at least 2+

For liver function tests, the number and percentage of subjects will be summarized by upper limit of normal (ULN) category as follows:

- ALT (alanine aminotransferase), AST (aspartate aminotransferase) and ALK-P (alkaline phosphatase) will be summarized by normal, $> 3 \times \text{ULN}$, $> 5 \times \text{ULN}$ and $> 10 \times \text{ULN}$.

Number of subjects who meet Hy's Law criteria (total Bilirubin $> 2 \times \text{ULN}$ and ALT or AST $> 3 \times \text{ULN}$) will be summarized and corresponding listing will be presented.

In addition, number of Subjects with Lymphopenia by Maximum NCI-CTCAE Toxicity Grade 1-4 will be summarized. A listing with all post-discontinuation lymphocyte counts from subjects who require additional lymphocyte count monitoring visits, as per the protocol, will also be provided.

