7. GENERAL STATISTICAL METHODOLOGY

In general, summary statistics (n, mean, SD, median, minimum, and maximum for continuous variables, and number and percentage of subjects in each category for categorical variables) will be provided by treatment group. All summary tables will be based on observed data, and missing values will not be imputed unless otherwise indicated. Measurements collected from unscheduled visits or repeated assessments will not be included in the by-visit summary tables or figures, but will be included in the derivation of the last post-baseline value during treatment, the analyses for the potentially clinically significant (PCS) post-baseline values, and subject listings. Source data for the summary tables and statistical analyses will be presented as subject data listings.

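### SAP 3.6.5 limits laboratory summaries to scheduled values without confining this to by-visit tables, so read literally it drops required repeat tests from the worst-value safety counts

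*SAP*

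**What the plan says.** SAP 3.6.5 opens its laboratory rules with: "Only scheduled laboratory parameters will be included in the summaries". The next sentence sends all laboratory data, including unscheduled results, to the listings. The section then plans several outputs that are not by-visit tables:

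- Boxplots: "Boxplots will be used to display summary statistics for the last assessment, maximum and minimum change from baseline values", for selected chemistry and hematology parameters.
- Shift tables from baseline to any post-baseline visit in the treatment period.
- PCS counts, with their own rule: "Clinical laboratory test values, scheduled or unscheduled, will be considered PCS if they meet PCS criteria listed in" SAP Table 2.
- Liver tests, where "the number and percentage of subjects will be summarized by upper limit of normal (ULN) category as follows": >3x, >5x and >10x ULN for ALT, AST and ALK-P.
- A count of subjects meeting Hy's Law (total bilirubin >2xULN with ALT or AST >3xULN).
- A lymphopenia table: "number of Subjects with Lymphopenia by Maximum NCI-CTCAE Toxicity Grade 1-4 will be summarized".

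SAP 7 gives the general rule. "Measurements collected from unscheduled visits or repeated assessments will not be included in the by-visit summary tables or figures", but such values "will be included in the derivation of the last post-baseline value during treatment", in the PCS analyses and in the listings. SAP 6.1 likewise keeps unscheduled visits out of by-visit statistics only.

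Protocol 7.2 requires AST or ALT >3xULN, and lymphocytes <0.5 x 10^9/L, to be "confirmed by repeat testing as soon as possible", with a further decision if the value persists for 4 weeks or more. Protocol 5.4 puts safety laboratory tests on the Unscheduled Relapse Visit list.

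**The concern.** The 3.6.5 sentence is wider than the two general sections and does not fit the PCS rule a few lines below it. It also gives a different input from SAP 7 for the last value, provided the last assessment in the 3.6.5 boxplots is the same quantity as SAP 7's last post-baseline value during treatment. The SAP does not say whether it is.

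The ULN-category, Hy's Law and maximum-grade tables count each subject's worst result, and the maximum and minimum change boxplots show extremes. The results most likely to be extreme include those drawn because a scheduled value crossed a threshold. If a programmer applies the 3.6.5 sentence as written, those results do not enter the outputs meant to show them. Long-term safety is the first objective of the study, so these counts matter.

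**Working it through.** The plan gives no figure to reproduce. The check sets the rules side by side, looks at the visit schedule, and follows one subject through both readings.

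**1. Which rule covers which output**

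| Output | 3.6.5 sentence, read literally | SAP 6.1 and SAP 7 |
|---|---|---|
| By-visit tables and figures | Scheduled only | Scheduled only |
| PCS counts | Scheduled only, but 3.6.5's PCS rule says both | Unscheduled included |
| Last-value boxplot | Scheduled only | Unscheduled included, if the same quantity |
| Maximum and minimum change boxplots | Scheduled only | Not named |
| Shift to any post-baseline visit | Scheduled only | Not named |
| ULN categories, Hy's Law, maximum grade | Scheduled only | Not named |

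The rules agree only on the first row. In the last three rows the 3.6.5 sentence is the only wording that could apply.

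**2. Would the required repeats be unscheduled?**

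Scheduled laboratory days on treatment (Protocol Table 1): 1, 15, 29, 57, 85, 113, 141, 169, 253, 337, 421, 505, 589, 673.

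- Gaps: 14 days (twice), 28 days (five times), 84 days (six times). Check: 2 x 14 + 5 x 28 + 6 x 84 = 28 + 140 + 504 = 672 = 673 - 1.
- Share of treatment time with 84-day gaps: 504/672 = 75%.
- Shortest such gap with the ±5-day windows: 84 - 5 - 5 = 74 days.

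A prompt repeat, or a recheck 28 days later, that follows a scheduled crossing in this stretch would normally fall between scheduled visits. Before Day 169 the gaps are 14 to 28 days, so a 4-week recheck could coincide with a scheduled visit.

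**3. One subject under the two readings (assumed values)**

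Scheduled ALT 4xULN; prompt unscheduled repeat ALT 8xULN.

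| Count | Scheduled only | All values |
|---|---|---|
| ALT >3xULN | Yes | Yes |
| ALT >5xULN | No | Yes |
| Largest ALT | 4xULN | 8xULN |

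The lymphocyte table behaves in the same way. With a scheduled count of 0.48 and a repeat of 0.18 x 10^9/L (assumed), the maximum grade would be set from 0.48 under one reading and from 0.18 under the other.

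This subject could be missing from the Hy's Law count only if bilirubin was also measured at the unscheduled draw and exceeded 2xULN.

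**4. Does the PCS table make up for it?**

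Only in part. The PCS cut-offs are ALT or AST >=3xULN and lymphocytes <0.5 x 10^9/L, practically the same as the Protocol 7.2 repeat-test triggers. A subject whose scheduled value set off the repeat has already met the PCS criterion, so a worse repeat adds nothing to that count. The PCS table has no >5x or >10x level, no grading, and no criterion joining ALT or AST to bilirubin. Its bilirubin limit is >=2 mg/dL, not a multiple of ULN. It does pick up a crossing seen only at an unscheduled visit, if the baseline value was non-PCS. In that case the PCS and ULN tables would disagree for the same subject.

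**The case against.** The strongest reply is that the SAP points to a by-visit meaning. The PCS counts are themselves summaries and use unscheduled values, so the sentence cannot cover every summary. It stands just before the by-visit chemistry and hematology tables. SAP 6.1 and SAP 7 both confine the exclusion to by-visit output, and that reading makes all three sections agree. This stands as the likely intention. It does not settle the matter. The sentence carries no such limit, it is specific to laboratory data while SAP 7 speaks in general terms, and SAP 7's list of outputs that take unscheduled values omits the tables at issue. The programming specifications and mock tables are separate documents that were not available, and they may already resolve it.

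The second reply is that nothing is hidden. The triggering scheduled value is still counted, all results are listed, the PCS listing shows every value of the parameter for a flagged subject, and a Hy's Law listing is planned. That also stands, but a listing does not correct a category count.

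Two stronger inferences are tempting and unsupported. A reader might infer that the required repeat would itself reveal Hy's Law cases that the table then loses. Protocol 7.2 names AST/ALT, lymphocytes, eGFR and the urine albumin to creatinine ratio for repeat testing, and does not name bilirubin. A reader might also take the 75% as a measure of the undercount. It describes how often a repeat would fall between scheduled visits, not how many subjects have a worse value there.

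**Conclusion.** The concern holds as an inconsistency in the written rules. The 3.6.5 sentence disagrees with its own PCS rule and with the by-visit scope of SAP 6.1 and SAP 7. It conflicts with SAP 7 on the last value if the two differently worded quantities are the same. Followed literally, it removes protocol-required repeats and relapse-visit laboratory results from the ULN-category, Hy's Law and maximum-grade tables and from the maximum and minimum change boxplots.

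The size is unknown. The documents give neither the frequency of unscheduled draws nor how often a repeat is worse than its trigger. Per subject, if about 1000 subjects have post-baseline laboratory data, one omission lowers an overall category by 1/1000 = 0.1 percentage points. Loss occurs only when the worst value is unscheduled, and only if the literal reading is the one programmed. The documents do not show that any case will be missed. They do show that the written rule allows it for outputs serving the first objective.

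**What to change.** In SAP 3.6.5, limit the scheduled-only sentence to by-visit summaries. Then state that these outputs use all post-baseline values, scheduled and unscheduled:

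- the last-assessment boxplot, kept to SAP 7's during-treatment limit and declared to be the same quantity;
- the maximum and minimum change boxplots;
- the tables of shift to any post-baseline visit, within the treatment period as planned;
- the ULN-category, Hy's Law and maximum CTCAE lymphopenia grade tables.

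Extend the inclusion list in SAP 7 to match.

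The cost is a few sentences and minor programming. No new data are needed. Some worst-value counts may look slightly less favourable.
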